## 5.4 Statistical Methods – Sample SAS Codes

### 5.4.1 Example SAS code for analysis using ANCOVA

```
PROC MIXED DATA=ADTSS;  
  CLASS ASTHCOPD TRT01P;  
  MODEL AUCTSS= TSSBASE ASTHCOPD TRT01P;  
  LSMEANS TRT01P/ DIFF CL;  
RUN;
```

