11. STATISTICAL CONSIDERATIONS

11.1 General Considerations

Statistical analysis of this study will be the responsibility of Enanta Pharmaceuticals, Inc. or its designee. Details of the statistical analysis methods will be described in the statistical analysis plan (SAP) document.

Continuous endpoints will be summarized using n, mean, standard deviation, median, 25th quartile, 75th quartile, minimum, and maximum values. Categorical endpoints will be summarized by the number of subjects meeting the endpoint and the percentage of subjects out of the appropriate population. The denominator will be displayed when needed. Statistical inference will be performed as appropriate. Inferential testing will be conducted using a two-sided alpha of 0.05, unless stated otherwise.

Any change to the data analysis methods described in the protocol will require an amendment if it changes a principal feature of the protocol. Any other change to the data analysis methods described in the protocol, and the justification for making the change, will be described in the clinical study report or SAP. Changes may only be made in the SAP prior to unblinding.

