11.2 Sample Size Considerations

Using a ratio of 1:1, a sample size of 27 subjects per treatment group (54 subjects total) provides 80% power to detect a treatment reduction in TSS AUC of at least 55% from placebo (assuming TSS AUC from the previous Phase 2a clinical challenge study to: mean [standard deviation]) of placebo: 500 [450] and EDP-938: 225 [200]) using a t-test with unequal variance. Assuming a 20% dropout rate, approximately 35 subjects per treatment group (approximately 70 subjects total) are needed.

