The TSS AUC from Day 1 through Day 14 will be calculated using the trapezoid rule (*Matthews et al., 1990*). The AUC will require at least 2 non-missing calculated total symptom scores. Missing total symptom score data will be reviewed for potential impact, and any decisions to include subjects that fail these criteria above will be documented. The AUC will be calculated based on available individual assessments of TSS collected twice per day from Day 1 through Day 14, and the actual date/time of each assessment will be used for the calculation. For the baseline TSS, the actual time is set as 0. For each assessment post first dose, the actual time in days is computed as difference between the date/time of the assessment and the date/time of the first dose. The AUC is also standardized for 14 days by multiplying  $14/t_{last}$  where  $t_{last}$  is the actual time in days of the last available assessment. Additionally, the AUC from Day 1 through Day 3, the AUC from Day 1 through Day 5, and the AUC from Day 1 through Day 9 will be also derived and standardized similarly as for AUC from Day 1 through Day 14.

The AUC TSS from Day 1 through Day 14 will be compared between EDP-938 and placebo using an analysis of covariance (ANCOVA) model with treatment group, asthma/COPD status (present or absent) as factors and the baseline TSS as a covariate. The analysis will be performed using SAS procedure MIXED. Treatment groups will be compared using a type III sum-of-squares. The least-squares means, standard errors and two-sided 95% confidence intervals (CI) will be presented for individual groups and the difference between groups. The same ANCOVA analysis will be performed for the TSS AUC from Day 1 through Day 3, from Day 1 through Day 5 and from Day 1 through Day 9.

Descriptive statistics will be displayed for TSS and change from baseline by day and timepoint and also for average daily TSS by day and will include at a minimum the number of non-missing measurements, mean, standard deviation, median, minimum, maximum, and 95% CI for the mean.

Multiple line graphs of TSS will be produced:

- (1) Observed mean TSS  $\pm$  95% confidence interval by days 1-14 and timepoint for each treatment group
- (2) Observed mean TSS (average per day)  $\pm$  95% confidence interval by days 1-14 for each treatment group

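### The sample size assumes SDs of 450 and 200, but the primary ANCOVA fits one residual variance, so the promised per-arm 95% intervals are miscalibrated under the plan's own figures

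*SAP*

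**What the plan says.** Protocol 11.2 states that "a sample size of 27 subjects per treatment group (54 subjects total) provides 80% power". The effect it is sized for is a TSS AUC 55% lower on EDP-938. The means and SDs behind that are given as "of placebo: 500 [450] and EDP-938: 225 [200]) using a t-test with unequal variance".

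SAP 3.14.1 makes the primary analysis an ANCOVA of TSS AUC in PROC MIXED with treatment, asthma/COPD status and baseline TSS. It adds that "The least-squares means, standard errors and two-sided 95% confidence intervals (CI) will be presented for individual groups", and also for the difference. The code in SAP 5.4.1 is "MODEL AUCTSS= TSSBASE ASTHCOPD TRT01P" followed by "LSMEANS TRT01P/ DIFF CL". It has no `REPEATED / GROUP=` statement and no robust (`EMPIRICAL`) option.

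In the visible text, neither document specifies a variance check, a transformation or a robust standard error for TSS AUC. The planned sensitivity analyses are multiple imputation and possibly a repeated-measures model (Protocol 11.6.2), and exclusion of scores close to acetaminophen use plus a Cox model for symptom resolution (SAP 3.14.1.1). None of them is directed at unequal variance in TSS AUC.

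**The concern.** The design and the analysis make opposite assumptions about the same quantity. The planning SDs imply a variance ratio of (450/200)² = 5.1. PROC MIXED without a grouped residual structure estimates one variance and uses it for both arms.

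That matters most for the per-arm least-squares means. If the arms differ as planned, the shared variance is too small for placebo and too large for EDP-938, whatever the arm sizes. These intervals are promised for the primary endpoint, and readers will use them to judge how precisely each arm's symptom burden is known. The treatment difference is less exposed, because at equal arm sizes the two errors cancel.

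**Working it through.** **Inputs.** Means 500 and 225, SDs 450 and 200, and 27 per arm for 80% power come from Protocol 11.2. Two-sided alpha 0.05 comes from Protocol 11.1. The 1:1 allocation is in SAP 3.4.

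**Reproducing the plan's figure.** The difference is 0.55 × 500 = 275. For a t-test with unequal variance at 27 per arm, the Satterthwaite df is 35.9 and noncentral-t power is 80.6%. At 26 per arm it is 79.0%. So 27 is the smallest sufficient size and the stated figure is reproduced.

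**Per-arm standard errors at 27 per arm, unadjusted.**
- Pooled SD = √((450² + 200²)/2) = 348.2; pooled SE = 348.2/√27 = 67.0 for both arms.
- Placebo, own variance: 450/√27 = 86.6.
- EDP-938, own variance: 200/√27 = 38.5.

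**Half-widths of the 95% interval.** Pooled: 2.007 × 67.0 = 134 in each arm. Own variance: 2.056 × 86.6 = 178 for placebo and 2.056 × 38.5 = 79 for EDP-938. The placebo interval is 25% too narrow (134/178 = 0.75) and the EDP-938 interval about 70% too wide (134/79 = 1.70).

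**Per-arm coverage.** With a pooled t on normal data (200,000 runs), coverage is 87.1% for placebo and 99.9% for EDP-938, at both 27 and 35 per arm. ANCOVA simulations of the least-squares means gave about 89% for placebo and 98% to 99% for EDP-938. The main ANCOVA run used 15,000 replicates, with an assumed baseline correlation of 0.3 and an assumed 20% with asthma/COPD.

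**Coverage of the interval for the difference.**

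| Placebo / EDP-938 | Pooled t | ANCOVA simulation | Separate variances |
|---|---|---|---|
| 27/27 | 94.7% | 94.9% | 94.9% |
| 35/35 | 94.8% | 95.1% | 95.0% |
| 33/37 | 93.9% | not run | 95.0% |
| 24/30 | 92.8% | 93.0% | 94.9% |
| 22/32 | 91.3% | 91.7% | 94.9% |
| 37/33 | 95.6% | not run | 95.0% |
| 30/24 | 96.4% | 96.4% | 95.0% |
| 32/22 | 97.2% | 97.1% | 95.0% |

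The direction depends on which arm is smaller. The unequal splits are illustrations; the documents give no expected split.

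**Power at 27 per arm, unadjusted.** Separate variances 80.6%, pooled 81.3%.

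**The case against.** Several arguments on the other side stand in whole or in part.

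- A reader might infer that the difference interval under-covers whenever the arms are unequal. It does not: it is conservative when placebo is the larger arm. A reader might also expect dropout and central RT-PCR exclusions to unbalance the arms. The documents do not show this. SAP 3.14.1 needs only two scores for an AUC, so most early leavers stay in, and PCR confirmation concerns the entry diagnosis. If 16 of 70 were lost at random, a placebo arm of 22 or fewer out of 54 would have probability 0.45%. Averaged over such random splits, pooled coverage is 94.7% to 94.8%.
- A reader might infer that the primary test is invalid. The planning figures have nearly constant coefficients of variation (450/500 = 0.90; 200/225 = 0.89). If that pattern holds, no treatment effect means equal SDs, and the pooled test keeps its level at any split. The miscalibration belongs to estimation when the effect is large.
- The planning SDs may not describe this endpoint. Protocol 4.2.2 describes the challenge-study score as a 10-point TSS; this trial uses 13 items. SAP 5.2 caps TSS at 39 and SAP 3.14.1 measures time in days, so a 14-day AUC cannot exceed 39 × 14 = 546. With mean 500 on that range the SD could be at most √(500 × 46) = 152. The SEs above are therefore on the planning scale. Coverage depends only on the SD ratio, so the coverage results carry over only if that ratio does.
- Skewness is not cured by separate variances. With gamma-distributed data they gave 93% to 94% for the difference, against 93.7% pooled at 27/27, so the gain at the planned split is small.
- The 5.4.1 code is labelled an example. True, but no other visible text specifies separate variances.

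None of this rescues the per-arm intervals, which are miscalibrated at equal arm sizes under the SDs that the plan itself adopts.

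**Conclusion.** The point holds for the per-arm intervals. Under SDs of 450 and 200, nominal 95% intervals cover about 87% to 89% for placebo and 98% to 99.9% for EDP-938, with no arm imbalance needed. For the treatment difference the effect is conditional: close to nominal at 1:1, about 94% at 33/37 and 93% at 24/30 if placebo is smaller, above 95% if placebo is larger.

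This rests on the planning SD ratio, on roughly normal data, and on the 5.4.1 code being what is run. The real ratio is unknown, which is a reason not to build equality into the model.

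Two extensions are tempting but not part of the point. Weighting the asthma/COPD strata by their observed mix (`OM` on `LSMEANS`) leaves the treatment difference unchanged, and the documents give no prevalence from which to size its effect on the per-arm means. Applying separate variances to viral load AUC has no planning SDs behind it.

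**What to change.** In SAP 3.14.1, state that the TSS AUC model estimates a separate residual variance for each arm. In SAP 5.4.1, add `REPEATED / GROUP=TRT01P;` and put `DDFM=KENWARDROGER` (or Satterthwaite) on the `MODEL` statement. The per-arm standard errors and intervals and the difference interval then all use arm-specific variances. The shorter-window TSS AUC analyses follow automatically, since 3.14.1 gives them the same model.

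If the sponsor prefers to keep the pooled model as primary, the minimum is to pre-specify the separate-variance model as a sensitivity analysis and take the per-arm intervals from it.

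The cost is one SAP sentence, two small code changes and under one point of power (80.6% against 81.3%, unadjusted, at 27 per arm). Protocol 11.1 allows SAP changes only before unblinding, so it must be done by then.

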### 5.4.2 Example SAS code for subgroup analyses using ANCOVA

```
ODS OUTPUT SLICES=SUBGRPLSM SLICEDIFFS=SUBGRPDIF;  
PROC MIXED DATA=ADTSS;  
  CLASS ASTHCOPD TRT01P SUBGRP;  
  MODEL AUCTSS= TSSBASE ASTHCOPD SUBGRP TRT01P TRT01P*SUBGRP;  
  SLICE TRT01PN*SUBGRP /SLICEBY=SUBGRP MEANS PDIF CL;  
RUN;
```
